10.6.2.3 Diarrhoea

Diarrhoea is an important identified risk for AZD4573, based on monkey preclinical toxicology studies and clinical data accumulated to date.

Participants with diarrhoea during therapy should be managed per Institutional guidelines with maximal supportive care and diagnostic evaluations as clinically indicated. After excluding infectious aetiologies, symptomatic management should be considered. Participants experiencing prolonged or severe diarrhoea should be closely monitored and managed as appropriate if dehydration and/or electrolyte abnormalities are observed.

Prophylaxis for diarrhoea with atropine is strongly recommended for all participants enrolled into the study as an anticholinergic drug, administered at 0.5 mg subcutaneously 15 to 30 minutes prior to all scheduled AZD4573 infusions. In the event of multiple episodes of diarrhoea despite atropine prophylaxis, 1 additional atropine dose may be considered and administered as outlined above. In addition, in the event of diarrhoea, participants should remain fully hydrated with additional intravenous fluids.

10.6.2.4 Nausea and Vomiting

Nausea and/or vomiting are important identified risks for AZD4573. Participants with nausea and/or vomiting during therapy should be managed per Institutional guidelines with maximal supportive care and diagnostic evaluations as clinically indicated. Participants experiencing prolonged or severe vomiting should be closely monitored and managed as appropriate if dehydration and/or electrolyte abnormalities are observed.

Events of nausea and vomiting have been observed in approximately half of all participants dosed with AZD4573, and have occurred at all dose levels tested to date (except 3 mg).

Prophylaxis with a 5-HT3 antagonist (e.g. ondansetron +/- dexamethasone) has been implemented in the Phase I study (D8230C00001) to help alleviate this toxicity.

Therefore, prophylaxis for nausea and vomiting is recommended as follows: administer dexamethasone 8 mg (IV administration preferable but orally also permitted) plus a 5-HT3 antagonist (eg, ondansetron initially 8 mg to be taken before treatment, then 8 mg every 12 hours for up to 3 days) as anti-emetics for all participants, approximately 30 to 60 minutes prior to all scheduled AZD4573 infusions. Additional doses of 8 mg dexamethasone may be administered if deemed clinically warranted. In addition, in the event of vomiting, participants should remain fully hydrated with additional fluids. Participants experiencing prolonged or severe nausea and vomiting should be closely monitored and managed as appropriate if dehydration and/or electrolyte abnormalities are observed.

10.6.2.5 Neutropenia and Febrile Neutropenia

Neutropenia and febrile neutropenia are important identified risks for participants treated with AZD4573. In the presence of CTCAE Grade 3/4 neutropenia, participant's blood counts should be monitored, using local laboratories, at least every 48 hours until recovery.

In the clinical setting to date, Grade 3/Grade 4 neutropenia (~ 45% to 50%) has been observed in several participants with an onset around 24 hours after dosing AZD4573 monotherapy. Usually, neutrophils recovered spontaneously even without G-CSF. However, colony-stimulating factors including G-CSF or pegylated G-CSF has been shown to work rapidly and may be used according to each investigator site's institutional guidelines. Anti-infective prophylaxis including anti-fungal prophylaxis should be used according to institutional guidelines. Anti-viral or cotrimoxazole prophylaxis may not be used unless CD4 helper cell counts are less than 100 to 200 per microlitre.

Primary prophylaxis with G-CSF is not generally recommended. Anti-infective prophylaxis (antibiotics and antifungals) should be given in accordance with local hospital guidelines and International National Comprehensive Cancer Network/European Society for Medical Oncology/American Society of Clinical Oncology guidelines.

10.6.2.6 Infection/Bone Marrow Toxicity with Peripheral Effect/Lymphoid Tissue Hypocellularity

Infection/Bone marrow toxicity with peripheral effect/lymphoid tissue hypocellularity is an important potential risk for AZD4573, based on findings in preclinical toxicology studies. As observed in preclinical studies, this important potential risk refers to haematological changes (decreased platelets, red blood cell count/haematocrit, reticulocytes, neutrophils, lymphocytes) that may be/may not be accompanied by secondary infections. AEs of thrombocytopenia should be managed as deemed appropriate by the investigator as per standard Institutional guidelines and in some cases, management of thrombocytopenia may require platelet transfusions; again, these should be done according to local hospital guidelines.

Common treatable causes of anaemia (e.g., iron, vitamin B12, or folate deficiencies and hypothyroidism) should be excluded. In some cases, management of anaemia may require blood transfusions which should be given as per local Institutional guidelines.

10.6.2.7 Pancreatic and Cortical Adrenal Injury (as well as Surveillance for Renal, Thymus, and Spleen Toxicity)

Pancreatic injury and cortical adrenal injury are potential risks for AZD4573 based on preclinical observations, however, to date, there are no clinical data suggestive of these risks, but safety surveillance will continue. Regular complete blood counts, clinical chemistry, and coagulation tests will be performed throughout the conduct of the study to monitor for any abnormal laboratory parameters, for example: monitoring of lipase and amylase levels for potential pancreas toxicity, creatinine values and regular urinalysis testing for kidney function, potassium, sodium, cortisol levels along with adrenocorticotrophic hormone levels for adrenal glands and TSH for any thyroid toxicity.

10.6.2.8 Drug-Drug Interactions

Drug-drug interactions is a potential risk for AZD4573 and refers to interactions with potent CYP3A4 inhibitors. Specific drug-drug interaction studies have not yet been performed for AZD4573.

Given the proposed clinical dosing regimen of AZD4573, a short IV infusion over 2 hours (once weekly), and the observed short half-life of approximately 4 to 7 hours, the risk of clinically meaningful drug interactions with AZD4573, is considered to be low.

In vitro studies suggest AZD4573 could reversibly inhibit cytochrome P450 (CYP)3A4/5, CYP2C8, CYP2C9, CYP2C19, organic anion transporting polypeptide (OATP)1B1, OATP1B3, organic anion transporter (OAT)1, OAT3, organic cation transporter (OCT)2 and multi-antimicrobial extrusion protein. However, clinical studies have not yet been performed to access the drug-drug interaction. Based on the static model recommended ([FDA 2017](#)), exposure increase of CYP3A sensitive substrates caused by AZD4573 will be 1.06, making it a weak inhibitor.

AZD4573 is not a strong inducer of CYP1A2, CYP2B6, or CYP3A, based on in vitro studies.

If potent CYP3A4 inhibitors are administered, it is recommended to avoid administering them on the same day as AZD4573 administration where possible. Alternatively, such inhibitors could be administered 8 to 12 hours after the completion of the AZD4573 infusion, if deemed clinically warranted in the opinion of the investigator. It is recommended that treatment with strong CYP3A4 inducers is avoided, unless it is deemed clinically warranted in the opinion of the investigator.

10.6.3 Criteria for Restarting Treatment

The criteria to be met before a participant receives further study drug infusions following a pause in treatment, either within 1 cycle or between cycles, is as below:

All participants:

- 1 Participant has recovered from all treatment-related non-haematological toxicity to CTCAE Grade ≤ 2 .
- 2 Recovery of neutrophils $> 1000/\mu\text{L}$ and platelets $> 75000/\mu\text{L}$ or $> 50000/\mu\text{L}$ with bone marrow involvement.
- 3 Participant has recovered from all hepatic toxicity events within the timeframes described in Table 12 above. If biochemical changes in transaminase(s) and total bilirubin are consistent with the definition of HL, the participant may continue to receive study drug only if all abnormalities have resolved within the timeframes specified in Table 5 above, there are no symptoms of liver injury and INR has not increased above $1.5 \times \text{ULN}$ (or $1.5 \times \text{baseline}$). In these circumstances the participant must be made aware of the unknown potential for liver damage with continued exposure to AZD4573 prior to retreatment. Documentation of continued consent is required.

- 4 Recovery of uric acid to < ULN.
- 5 Recovery of changes in uric acid, potassium, phosphorus, creatinine or calcium, or symptoms suggestive of TLS as defined in [Table 11](#).

10.7 Discontinuation of Study Intervention and Participant Discontinuation/Withdrawal – Module 1

See the SoA (Section [10.1.2](#)) for data to be collected at the time of intervention discontinuation and follow-up and any further evaluations that need to be completed.

Please refer to Section [7](#) (Core protocol) for information on discontinuation of study intervention and participant discontinuation/withdrawal.

10.8 Study Assessments and Procedures – Module 1

- Study procedures and their timing are summarised or linked to in the SoA. Protocol waivers or exemptions are not allowed.
- Immediate safety concerns should be discussed with the sponsor immediately upon occurrence or awareness to determine if the participant should continue or discontinue study intervention.
- Adherence to the study design requirements, including those specified in the SoA, is essential and required for study conduct.
- All screening evaluations must be completed and reviewed to confirm that potential participants meet all eligibility criteria. The investigator will maintain a screening log to record details of all participants screened and to confirm eligibility or record reasons for screening failure, as applicable.
- Procedures conducted as part of the participant's routine clinical management (eg, blood count) and obtained before signing of the ICF may be utilised for screening or baseline purposes provided the procedures met the protocol-specified criteria and were performed within the time frame defined in the SoA.
- The maximum amount of blood collected from each participant over the duration of the study, including any extra assessments that may be required, is not anticipated to exceed 436.5 mL in Cycle 1 (cycle duration of 5 weeks) and 124 mL in each subsequent cycle (cycle duration of 3 weeks).

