Non-haematological toxicities (except liver dysfunction and TLS)			

Event ^a	Occurrence	Action with AZD4573
Grade 3 or 4 non-haematological toxicities	First occurrence	
Withhold dosing with AZD4573 until the toxicity has resolved to Grade 1, but no longer than 21 days^b.
 
Adequate supportive therapy as per Institutional guidelines should be given.
 
After resolution of Grade 3 event to Grade 1, AZD4573 therapy may be resumed at the same dose. No dose modification is required.
 
After resolution of Grade 4 event to Grade 1, reduce dose by one dose level when re-starting AZD4573.

	Second occurrence	
Withhold dosing AZD4573 up to 21 days^b.
 
Adequate supportive therapy as per Institutional guidelines should be given.
 
After resolution to Grade 1, reduce dose by one dose level when re-starting AZD4573.
 
If no resolution within 21 days discontinue AZD4573^b.

	Third occurrence	Discontinue AZD4573.
Haematological Toxicities		
Grade 3 or 4 neutropenia without fever or infection, lasting > 7 days despite growth factor support	First occurrence	
Withhold dosing AZD4573 until Grade \leq 2 or baseline level.
 
Restart at same dose level following resolution.

	Second and subsequent occurrences	
Withhold dosing AZD4573 until Grade \leq 2 or baseline level.
 
Restart with 1 dose level reduction following resolution.
 
In case of subsequent occurrences, dosing may be modified to skip weekly dose(s) (eg, 2 weeks on/1 week off or to 1 week on/1 to 2 weeks off), after discussing with the Study Physician.

Grade 3 or 4 neutropenia with infection or fever	First occurrence	
Withhold dosing AZD4573.
 
To reduce the infection risks associated with neutropenia, G-CSF may be administered with AZD4573 if clinically indicated/required as per Institutional practice.
 
Consider secondary prophylaxis with G-CSF as per ASCO/ESMO guidelines. Once the toxicity has resolved to \leq Grade 2 or to baseline level, AZD4573 therapy may be resumed at the same dose.

	Second occurrence	
Withhold dosing AZD4573.
 
Consider using G-CSF as clinically indicated/as per Institutional practice. Follow dose reduction guidelines when resuming treatment with AZD4573 after resolution.
 
Reduce dose by 1 dose level.

Event ^a	Occurrence	Action with AZD4573
	Third occurrence	Discontinue AZD4573.

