Grade 3 thrombocytopenia without bleeding	Any	Withhold AZD4573 until Grade \leq 2 or baseline level. Restart AZD4573 at the same dose level.
Grade 4 thrombocytopenia without bleeding requiring blood or platelet transfusion	First occurrence	Withhold AZD4573 until Grade \leq 2 or baseline level. Restart AZD4573 at the same dose level.
	Second occurrence	Withhold AZD4573 until Grade \leq 2 or baseline level. Restart AZD4573 with 1 level dose reduction. If not recovered to Grade \leq 2 or baseline level discontinue.
	Third occurrence	Discontinue AZD4573.
Grade 3 or 4 thrombocytopenia with bleeding requiring blood or platelet transfusion	First occurrence	Withhold AZD4573 until Grade \leq 2 or baseline level. Restart AZD4573 with 1 level dose reduction. If not recovered to Grade \leq 2 or baseline level discontinue.
	Second occurrence	Discontinue AZD4573.

^a Adverse reactions are graded using NCI CTCAE version 5.0.

^b In cases where more than 21 days are needed, a decision to continue, modify, or discontinue study treatment will be made on a case-by-case basis in consultation with the principal investigator and the Study Physician.

Abbreviations: ANC, absolute neutrophil count; ASCO, American Society of Clinical Oncology; ESMO, European Society for Medical Oncology; G-CSF, granulocyte-colony stimulating factor.

Dose modifications for AZD4573 for abnormal liver chemistry test results are described in [Table 12](#).

Table 12 Recommended Dose Modifications for AZD4573 for Abnormal Liver Chemistry Test Results

Event ^a	Action
Isolated^b elevations in ALT, AST, or bilirubin	
Grade 1 Isolated ALT/AST \leq 3 \times ULN or Isolated Bilirubin \leq 1.5 \times ULN	Maintain current dose level. Monitor ALT, AST, ALP, and bilirubin at least 1x per week.

Event ^a	Action
Grade 2 Isolated ALT/AST > 3 to $\leq 5 \times$ ULN or Isolated Bilirubin > 1.5 to $\leq 3 \times$ ULN	After 7 days if hepatic enzymes resolve to Grade ≤ 1 , re-challenge at same dose level.
Grade 3 Isolated ALT/AST > 5 to $20 \times$ ULN	If recovered to Grade ≤ 1 within 7 days, allow re-challenge at same dose level. If not recovered to baseline level within 7 days, discontinue AZD4573.
Grade 3 Isolated Bilirubin > 3 to $10 \times$ ULN	If recovered to baseline level within 96 hours (-2/+12 hours) of start of dose allow re-challenge at same dose level. If not, discontinue AZD4573.
Grade 4 Isolated ALT > $20 \times$ ULN or Isolated Bilirubin > $10 \times$ ULN	Discontinue AZD4573.

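### Section 10.6.3 and Table 11 of the protocol set different recovery levels for restarting AZD4573 (non-haematological Grade 2 versus Grade 1, and platelets), and no text says how the two combine.

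*Protocol*

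**What the plan says.** **Section 10.6.3** applies to all participants, within or between cycles, and gives "The criteria to be met before a participant receives further study drug infusions following a pause in treatment". Two of its five items matter here.

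- Item 1: "Participant has recovered from all treatment-related non-haematological toxicity to CTCAE Grade" 2 or lower.
- Item 2: platelets above 75000/µL, or above 50000/µL "with bone marrow involvement" (with a neutrophil level as well).

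**Table 11 in Section 10.6.1**, in the row for Grade 3 or 4 non-haematological toxicity other than liver dysfunction and TLS, says:

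- First occurrence: "Withhold dosing with AZD4573 until the toxicity has resolved to Grade 1, but no longer than 21 days". For a Grade 3 event, "After resolution of Grade 3 event to Grade 1, AZD4573 therapy may be resumed at the same dose"; a Grade 4 event restarts one level lower, also after Grade 1.
- Second occurrence: "After resolution to Grade 1, reduce dose by one dose level when re-starting AZD4573". If there is no resolution within 21 days the drug is discontinued. Footnote b allows a case-by-case decision beyond 21 days.
- Third occurrence: discontinue.

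For platelets, in the row for "Grade 3 thrombocytopenia without bleeding", Table 11 holds the drug until Grade ≤ "2 or baseline level. Restart AZD4573 at the same dose level". The other thrombocytopenia rows use the same recovery level wherever a restart is allowed. None separates participants by marrow status.

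Four other places bear on the question. Core Section 7.1 ties restarting to the module's dose modification and discontinuation guidelines. The text of Section 10.6.1 allows a restart when toxicity resolves as those guidelines describe. Core Section 6.6 requires discussion with the Study Physician before dosing resumes. Footnote c of the Schedule of Activities, repeated in Section 10.8.2.5, applies inclusion criteria 10, 13 and 14 at the start of every cycle and adds that the Section 10.6.1 guidelines also apply.

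**The concern.** Both passages are current Module 1 text, both concern resumption after a pause, and they name different recovery levels. Items 3 and 5 of Section 10.6.3 refer back to Tables 12 and 11. Items 1 and 2 refer to nothing and give thresholds of their own. An investigator who reads Section 10.6.3 as the restart rule, and one who reads Table 11 as the restart rule, can reach different decisions for the same participant. The study plans about 30 centres.

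What is at stake is re-dosing after Grade 3 or 4 toxicity, and the tolerability data that follow from it. Discontinuations for related AEs count towards the > 25% trigger for SRC evaluation (Sections 7.1.1, 10.4.1 and 10.4.4). The SRC also has to confirm in each cohort whether the 12 mg weekly regimen is tolerable. SAP Section 5.6.1 summarises dose delays, actual exposure and relative dose intensity, and SAP Section 4.1.3.5 lists departure from the prescribed dosing regimen as a deviation category. Each depends on what the prescribed restart rule is.

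**Working it through.** The protocol gives no figure to reproduce, so the check sets the rules side by side and follows them through examples.

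**1. Non-haematological toxicity, after a treatment-related Grade 3 or 4 event (not liver, not TLS), first or second occurrence**

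| Current grade | Section 10.6.3 item 1 | Table 11 |
|---|---|---|
| 3 or 4 | not met | hold |
| 2 | met | hold |
| 1 | met | restart allowed |

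The rules differ at Grade 2 only. A Grade 2 toxicity that was never worse creates no conflict, because Sections 10.6.1 and 10.6.2 generally require no dose modification for it.

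**2. Effect on a dose delay (hypothetical first Grade 3 event).** Last dose on Day 1, Day 8 dose held, Grade 2 by Day 15, Grade 1 by Day 22. SAP Section 5.6.1.1 defines the delay as date of first dose after the delay − date of last dose before it − 9.

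- Restart when item 1 is met: 15 − 1 − 9 = 5 days.
- Restart when Table 11 is met: 22 − 1 − 9 = 12 days.

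SAP Section 5.6.1.2 counts delays below 7 days and of 7 days or more separately, so the same clinical course falls in different categories.

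**3. Effect on discontinuation (hypothetical second Grade 3 event).** Hold from Day 8, Grade 2 by Day 15, still Grade 2 when 21 days have passed on Day 29.

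- Item 1 alone: the Day 8 dose is missed; the Day 15 and Day 22 doses are not barred by that item.
- Table 11: the doses due on Days 8, 15 and 22 are missed (21/7 = 3). The drug is then discontinued unless a case-by-case decision is made under footnote b.

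**4. Effect on the SRC trigger (illustration).** Pooled monitoring starts from the initial 15 dosed patients. Three related discontinuations give 3/15 = 20.0%, and four give 4/15 = 26.7%. At that size, one participant discontinued under one reading and continued under the other could decide whether 25% is exceeded. The documents do not say how often this would occur.

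**5. Platelets.** Let C be the lower limit of CTCAE v5.0 Grade 2, which the documents do not print. Table 11 allows restart at the lower of C and baseline, whatever the marrow status. Item 2 requires more than 75000/µL without marrow involvement, or more than 50000/µL with it.

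- If C is below 75000, participants without marrow involvement with counts from C to 75000 satisfy Table 11 and fail item 2.
- If C is 75000 or more, participants with marrow involvement and a baseline above 50000 can satisfy item 2 before they satisfy Table 11.

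No value of C makes the rules agree, so the difference follows from the documents alone. Its location depends on C. **Assuming C = 50000/µL**, the gap is 50000 to 75000/µL without marrow involvement, and Section 10.6.3 is the stricter rule. With marrow involvement the two then differ only at exactly 50000.

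**6. Cycle starts.** Inclusion criterion 13 requires at least 75000/µL without marrow involvement, or at least 50000/µL with it. Because footnote c applies this at every cycle start, counts below 75000 without marrow involvement are already barred there. The platelet gap therefore matters mainly for restarts within a cycle. Those laboratory criteria do not set a general recovery grade for non-haematological toxicity, so they do not settle step 1.

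**The case against.** The strongest answer is that the two rules are cumulative. Section 10.6.3 lists conditions to be met; it neither orders nor grants a dose. Meeting item 1 does not lift a Table 11 hold, and a site can comply with both by waiting for the later one. Item 1 also has a wider scope: all treatment-related non-haematological toxicity, including events that coexist with the one that caused the pause. Sections 7.1 and 10.6.1 point to the dose modification guidelines, and Section 6.6 puts a Study Physician discussion before resumption.

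Much of this stands. A reader might infer that a participant at Grade 2 is both to be dosed and not to be dosed. The documents do not support that, because Section 10.6.3 compels no infusion and its other items must also be met.

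The ambiguity remains all the same. The cumulative reading is stated nowhere for items 1 and 2. Sections 7.1 and 10.6.1 refer to guidelines in the module without ranking Section 10.6.3 against Table 11. Outside liver dysfunction and TLS, a toxicity that fails item 1 is Grade 3 or worse and would already be on hold under Table 11. Read cumulatively, item 1 then adds almost nothing, which invites reading it as the operative restart level. The Study Physician discussion reduces divergence between sites, but the physician works from the same two texts.

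**Conclusion.** The point holds as an internal inconsistency that leaves the restart rule open to two readings. It concerns treatment-related Grade 3 or 4 non-haematological events, excluding liver dysfunction and TLS, that have improved to Grade 2 and not yet to Grade 1. It also concerns platelet recovery, mainly within cycles. The 50000 to 75000/µL band rests on the assumed Grade 2 limit of 50000/µL; the existence of a platelet difference does not.

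The outputs affected are time off drug, some treatment-related discontinuations and hence the > 25% SRC trigger, dose delays and relative dose intensity. The number of participants affected cannot be estimated from the documents.

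Two wider inferences are not supported. Dose-reduction steps do not depend on the reading, because only Table 11 sets them. The ORR analysis, sample size and analysis sets are untouched. The point is still worth correcting, since it governs re-dosing after severe toxicity in a trial with no formal data monitoring committee and the correction costs little.

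**What to change.** Reconcile items 1 and 2 of Section 10.6.3 with Table 11, and with the cycle-start criteria in footnote c of the Schedule of Activities and Section 10.8.2.5. Any of three forms would do: one recovery grade and one platelet level used throughout; a cross-reference from items 1 and 2 to Table 11, as items 3 and 5 already have; or a sentence saying that the rules apply cumulatively, or which governs. The sponsor and the SRC choose the values; this review proposes none.

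The same edit should check item 3 of Section 10.6.3, which cites Table 5 for hepatic timeframes although Table 5 holds the haematological entry criteria.

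The cost is a wording correction in an amendment or clarification letter, with no added participants, assessments or analyses. If participants have already restarted under either reading, the deviation specifications should say how those restarts are classified before database lock.
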